PROTOCOL TITLE: Transversus abdominus plane (TAP) block catheters vs liposomal bupivacaine for pain control after colorectal surgery: A prospective randomized control trial

1) Protocol Title

Transversus abdominus plane (TAP) block catheters vs liposomal bupivacaine for pain control after colorectal surgery: A prospective randomized control trial

Protocol Version Date: 1/31/17

2) Objectives

- i) Primary: Compare the use of TAP blocks with ropivacaine bolus and ropivacaine catheters versus single shot TAP blocks with liposomal bupivacaine
 - (1) We anticipate superior efficacy and pain control with liposomal bupivacaine TAP blocks measured by use of opioids (measured in oral morphine equivalents) in the first 48 hours following surgery.
- ii) Secondary:
 - (1) Assess the efficacy and safety of TAP blocks for pain control after colorectal surgery in a prospective fashion
 - (a) Hypothesis: Anticipate satisfactory pain control in both TAP block groups for somatic abdominal pain measured as proportion of pain scores in the mild range (up to 4 out of 10 pain documented in nursing notes)
 - (b) Anticipate equivalent side effects measured as duration of ileus, rash, itching, nausea/vomiting.
 - (2) Compare the pharmacological costs and medical utilization costs of TAP block catheters versus single shot injection of TAP block with liposomal bupivacaine
 - (a) Anticipate lower medical utilization costs with single shot injection with liposomal bupivacaine TAP blocks
 - (b) Measured as acquisition cost of drugs and supplies

3) Background

Pain control after abdominal laparoscopic surgery involves multiple components of somatic and visceral pain. Although opioids are commonly used for acute postoperative pain control, opioid – induced constipation that can increase the risk of postoperative ileus, nausea, and pruritus are significant side effects that may prolong hospital length of stay. Multimodal analgesic regimens have been shown to increase pain control while sparing the use of systemic opioids. These have included modalities such as acetaminophen, non-steroidal anti-inflammatory drugs, and peripheral nerve blocks.

The transversus abdominus plane block (TAP) is a minimally invasive ultrasound guided peripheral nerve block that is helpful in decreasing somatic abdominal pain after surgery

PROTOCOL TITLE: Transversus abdominus plane (TAP) block catheters vs liposomal bupivacaine for pain control after colorectal surgery: A prospective randomized control trial

and decreases opioid consumption while improving pain control. TAP involves local anesthetic infiltration between the internal oblique and the transversus abdominis plane in which space the terminal branches of the anterior roots of the lower six thoracic and first lumbar nerves course. These nerves innervate the anterolateral abdominal wall. In colorectal surgery patients, TAP have resulted in a decrease in 24-hour morphine consumption as well as earlier discharge and return to diet time compared to patient controlled analgesia (PCA).

At UC Davis, it is standard practice to place TAP blocks with catheters for adult colorectal surgery patients for perioperative pain control. In many cases, the TAP catheters will remain in the patient for two days and are removed when the patient's somatic pain is controlled and they are able to tolerate oral intake. However, it is resource intensive requiring the use of two sterile peripheral nerve catheter kits, two CADD infusion pumps, nursing time to replace the ropivacaine infusion cassette every 8-10 hours, and 30-40 minutes of physician time for block placement with additional physician time needed for ongoing catheter management. There is also a risk of catheter – related complications including inadvertent dislodgement, catheter infections, and increased burden to the patient from the two additional catheters tethered to the patient.

An alternative TAP can be performed using liposomal bupivacaine (Exparel). This is an extended release local anesthetic that has been shown to last 48-72 hours and is FDA approved for surgical plane infiltration including TAP blocks, as detailed in a 2015 FDA letter. Although the expense of the Exparel is higher than a vial of ropivacaine, it is not clear that patients will receive equivalent pain control and satisfaction with one time Exparel TAP blocks as compared to TAP catheters with ropivacaine for the first 48-72 hours. Further, the costs and medical utilization related to TAP catheters may be greater than that of one vial of Exparel used for TAP blocks. Although there have been smaller studies showing the efficacy of Exparel for TAP blocks, there is currently no prospective study that evaluates the efficacy of single injection TAP blocks with Exparel compared to ropivacaine TAP catheters for colorectal surgery patients.

This study is designed to assess the comparative efficacy and cost of these two approaches. Results from this study will be significant to the fields of anesthesiology, acute pain management and colorectal surgery. With this prospective study, we will have concrete data on the use of single shot Exparel TAP blocks and TAP catheters to improve patient care at UC Davis and educate other institutions.

References:

Feierman, Dennis E., et al. "Liposomal bupivacaine infiltration into the transversus abdominis plane for postsurgical analgesia in open abdominal umbilical hernia repair: results from a cohort of 13 patients." *Journal of pain research* 7 (2014): 477.

PROTOCOL TITLE: Transversus abdominus plane (TAP) block catheters vs liposomal bupivacaine for pain control after colorectal surgery: A prospective randomized control trial

Walter, Catherine J., et al. "A randomised controlled trial of the efficacy of ultrasound-guided transversus abdominis plane (TAP) block in laparoscopic colorectal surgery." *Surgical endoscopy* 27.7 (2013): 2366-2372.

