Postoperatively, patients will be monitored in the PACU per routine care. Patients will be ordered a combination of standardized short acting opioids (fentanyl), and long acting opioids (hydromorphone) in addition to anti-emetics (ondansetron 4mg IV) for administration if needed in the PACU. In the PACU, perioperative nursing staff will dose medications accordingly to the EMR orders and the PACU clearance time will be logged as well. PACU duration is calculated as the time interval between patient arrival into the PACU and when the patient is signed out of the PACU by the PACU anesthesiology resident/faculty.

PROTOCOL TITLE: Transversus abdominus plane (TAP) block catheters vs liposomal bupivacaine for pain control after colorectal surgery: A prospective randomized control trial

Post-PACU hospital course will proceed as is standard of care with PRN pain medication. Patient with single shot Exparel TAP blocks will be seen on the inpatient floor for two days after the surgery to assess for postoperative pain control. Patients with TAP catheters will also be seen daily until the catheters are removed by the acute pain service and when the patient is tolerating an oral diet and there are no overt signs of postoperative ileus. Standard hospital discharge criteria will be used for both groups.

Information will be collected from the patients' hospital stays, including Ultrasound imaging of the patient's TAP block, intraoperative anesthesia record, the amount of opioid use in morphine oral equivalents in the first 6, 12, 18, and 24, 36, and 48 hours after surgery, incidence of nausea/vomiting, pain score averages from EMR Epic RN Pain data, PACU clearance time and length of hospital stay.

8) Data and/or Specimen Management and Confidentiality

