During the study phase, patient information will be stored electronically via a password protected database on the UC Davis OneDrive cloud storage folder. Only authorized study staff will have access to the file while access to the UC Davis OneDrive folder requires UC Davis login. Patients' information will be stored on a secure database with indirect identifiers, such as patient 1, patient 2, etc. There will be a separate password protected document that contains the indirect and direct identifiers to match the two. After the study has been closed, consents will be maintained for three years, and HIPAA consents for six years, in compliance with IRB rules and regulations. Any data obtained from the Electronic Medical Record (EMR) will be identified by subject ID only and collected onto an encrypted spreadsheet on the PI's password protected computer.

Statistical analysis plan & Sample size calculation

The primary outcome measure will be the between group difference in opioid consumption in the first 48 hours surgery.

We anticipate superior pain control in the Exparel group based on the potential for TAP catheter problems such as catheter dislodgement and lack of timely infusion refill. A difference in 20% of opioid oral morphine equivalents will be considered clinically significant. Prior reports (Carney et al) suggest a difference of $55.3\text{mg} \pm 17.6$ in the control group versus $26.8\text{mg} \pm 19.8$ in the TAP block group. Using a power of 0.8 and $p < 0.05$ as statistically significant yields a sample size of 44 per group to show significance. We will enroll 100 to allow for early withdrawal or protocol violations, with planned interim analysis at $n=20$ of each group completing the study (40 patients) to allow sample size refinement as needed. Data will be analyzed for normal distribution. Normally distributed data will be compared using a T-test for the 2 groups; data that is not normally distributed will be compared using the Mann Whitney U test. Categorical data will be compared by Chi square.

PROTOCOL TITLE: Transversus abdominus plane (TAP) block catheters vs liposomal bupivacaine for pain control after colorectal surgery: A prospective randomized control trial

All data will be stored online in the secure UC Davis OneDrive folder with password protected files. All research staff will have completed HIPAA – related training and IRB – related training.

9) Provisions to Monitor the Data to Ensure the Safety of Subjects

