Patients will be monitored closely in the PACU prior to discharge to the inpatient floor for any signs and symptoms of local anesthetic toxicity, abdominal pain, or allergic reaction. The dose of local anesthetic given will be calculated to be less than the toxic dose level for ropivacaine (2-3mg/kg) and liposomal bupivacaine (2-3mg/kg). Patients receiving TAP catheters will be seen daily by the acute pain service who will visually inspect the site of insertion and assess the patient for any abdominal pain.

Any adverse events, such as intravascular injection, allergic reaction, or other unanticipated event will be assessed for its causative relationship to the TAP block by the PI ([name]).

If a serious adverse event occurs, it will be reported immediately to the IRB and will trigger an immediate suspension in enrollment and a review of the injection protocol with the Chiefs of both the Departments of Anesthesiology and Colorectal Surgery. If any performer error can be identified and corrected, then with approval from the departments enrollment will continue. If not, the study will be terminated.

Any unexpected adverse events will be documented and reported to the IRB as well as study participants.

We will cumulatively review the data after 20 subjects in each study arm have been enrolled, and then again at 50 patients, 75 patients, 100 patients until study completion. Data will be reviewed for any adverse effects from TAP blocks, pain scores, opioid consumptions, other additional secondary outcome measures such as nausea/vomiting.

PROTOCOL TITLE: Transversus abdominus plane (TAP) block catheters vs liposomal bupivacaine for pain control after colorectal surgery: A prospective randomized control trial

10) Withdrawal of Subjects

Because this is a study comparing a single injection versus a peripheral nerve catheter, patients receiving a single injection are able to withdraw voluntarily any time prior to the injection. If there was difficulty with visualization of the TAP plane with ultrasound due to body habitus, then the patient will be withdrawn from the study. At all instances, patient safety will be the primary priority above all over study parameters.

With the TAP catheter group, patients may withdraw voluntarily from the study if they wish.

11) Risks to Subjects

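### Two secondary aims do not match the stated tests and data list: equivalent side effects have no margin or interval rule, and listed pain averages do not give the mild-score proportion

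*Combined protocol and SAP*

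**What the plan says.** **Side effects.** Section 2 (Objectives), secondary aim (1)(b), reads "Anticipate equivalent side effects measured as duration of ileus, rash, itching, nausea/vomiting". The section headed Statistical analysis plan & Sample size calculation gives the tests: "Normally distributed data will be compared using a T-test for the 2 groups", the Mann-Whitney U test for data that are not normal, and "Categorical data will be compared by Chi square". No equivalence margin, interval criterion or equivalence test appears anywhere. The only difference called clinically significant is 20%, and it concerns opioid use.

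**Pain control.** Secondary aim (1)(a) expects satisfactory control in both groups, "measured as proportion of pain scores in the mild range (up to 4 out of 10 pain documented in nursing notes". Section 7 (Procedures Involved) lists the information to be collected, including "incidence of nausea/vomiting, pain score averages from EMR Epic RN Pain data, PACU clearance time and length of hospital stay". The list is introduced as an inclusion, so it is not closed. It does not name individual pain scores, ileus duration, rash or itching.

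**Monitoring.** Section 9 says "Data will be reviewed for any adverse effects from TAP blocks, pain scores, opioid consumptions, other additional secondary outcome measures such as nausea/vomiting". It gives no summary measure for pain and no method for judging equivalence. It also sets the timing of the first look: "We will cumulatively review the data after 20 subjects in each study arm have been enrolled".

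**The concern.** The two gaps are separate.

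1. The tests named look for a difference, and failing to find one in a small trial is not evidence that the arms are alike. If (1)(b) is meant literally, the plan contains no rule by which it could be met. The only result it would produce in that direction is a non-significant p-value, which does not bear that meaning.

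2. The pain objective is defined on individual scores (how many are 4 or less), but the summary listed for collection is an average. If staff abstract what section 7 names and nothing more, the stated measure cannot be calculated afterwards without returning to the chart.

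At stake are the side-effect statement and the pain-control statement in the eventual report. The primary outcome, opioid use over 48 hours, does not depend on either.

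**Working it through.** **Inputs from the documents:** 44 per group, 100 to be enrolled (about 50 per arm if allocation is equal, which is assumed), p < 0.05 (two-sided assumed), and the 4/10 cut-off. **Assumed, because the documents give none:** side-effect incidences of 5% to 40%, and a margin of ±20 points.

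**The plan's own figure.** The sample size concerns opioid use only. Difference = 0.20 × 55.3 = 11.06 mg. Pooled SD = √((17.6² + 19.8²)/2) = 18.73. n = 2 × (18.73 × (1.960 + 0.842)/11.06)² ≈ 45.0, rounded up to 46. With the simple mean of the two SDs, 18.7, n = 44.9, rounded up to 45. Both are within 2 of the stated 44. Nothing in this calculation concerns side effects.

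**1. What a non-significant side-effect result would mean**

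*Power of the planned test.* Every pair of counts (x₁, x₂) was enumerated from two binomials with 44 per arm, adding the probabilities where the uncorrected chi-square rejects.

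- 10% v 20%: power 0.270. A doubled rate would go undetected about 73% of the time.
- 30% v 45%: power 0.319.
- At 50 per arm these become 0.303 and 0.344.

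*Precision.* The half-width of the 95% interval for a risk difference is 1.96 × √(2p(1−p)/44). At p = 0.10 this is 1.96 × √(0.18/44) = 0.125. At p = 0.40 it is 1.96 × √(0.48/44) = 0.205.

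*Chance that the interval lies inside ±20 points when the true rates are equal* (exact enumeration, Wald interval, 44 per arm):

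| Assumed incidence | 95% interval | 90% interval |
|---|---|---|
| 5% | 96% | not tabulated |
| 10% | 76% | 84% |
| 20% | 32% | 54% |
| 30% | 9% | 31% |
| 40% | 2% | 26% |

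The 90% column corresponds to two one-sided tests at 5%. At 50 per arm the 95% figures for 10% to 40% incidence are 83%, 43%, 18% and 8%.

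*Ileus duration.* No SD is given, so only SD units are possible. The half-width is 1.96 × √(2/44) = 0.42 SD. The margin needed for an 80% chance of success is (1.960 + 1.2816) × √(2/44) = 0.69 SD.

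**2. Whether an average determines the proportion of scores up to 4**

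Take integer scores 0–10 and let q be the proportion that are 4 or less.

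- *Lower bound.* Mild scores are at least 0 and the others at least 5, so mean ≥ 5(1−q), giving q ≥ 1 − mean/5. For a mean of 4.0, q ≥ 0.20, reached by one score of 0 and four of 5.
- *Upper bound.* For a mean of 4.0, every score can be 4, so q = 1.00.

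A mean of 4.0 is therefore compatible with 20% to 100% mild scores. A less extreme case makes the same point: 0, 0, 0, 0, 6, 6, 7, 7, 7, 7 has mean 40/10 = 4.0 and 40% mild, while ten scores of 4 have the same mean and 100% mild. The proportion cannot be recovered from the average.

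**The case against.** **The word may be informal.** The sentence is an expectation, parallel to those about satisfactory pain control and lower costs. Section 3 (Background) uses the word loosely too: "it is not clear that patients will receive equivalent pain control and satisfaction". A reader might infer that the investigators plan to declare equivalence from a non-significant test. The documents do not say so; no equivalence conclusion or decision rule is written. If similar was meant, the defect is one of wording. This stands, and it limits the point, but the plan does not say which meaning applies.

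**These aims are not listed as endpoints.** Section 6 names only time to PACU discharge and to hospital discharge as secondary endpoints. That favours a descriptive reading of (1)(a) and (1)(b), and a descriptive remedy fits it.

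**The pain data should exist.** The section 7 list is open, the objective already names nursing notes as the source, and section 9 refers to pain scores, not averages. A reader might infer that the mild-score proportion is unobtainable. It is not: the individual scores should be in the same nursing record. What stands is that the one pain summary named for collection is not the one the objective needs.

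**Averages could reverse the arms.** This is tempting, since extreme score patterns allow it arithmetically. But (1)(a) expects satisfactory control in both groups and ranks neither, so reversal would not damage the stated aim, and nothing in the documents suggests such patterns are likely.

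**The sizes are assumed.** They are. At 5% incidence the interval falls inside ±20 points 96% of the time, and a 90% interval raises every figure where both were calculated. It would be wrong to say that equivalence is out of reach for every side effect.

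**Conclusion.** Both mismatches are in the text. The planned tests cannot support a literal claim of equivalent side effects, and the listed pain averages do not yield the stated pain measure. The first is at least a wording fault, and becomes a substantive one only if equivalence is really to be claimed. The second is a gap in what staff are told to abstract, not in what the chart holds.

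The pain result is arithmetic and needs only integer scores. The side-effect figures rest on assumed incidences and an assumed ±20-point margin. They show that, with this sample size, equivalence within that margin is realistic for uncommon events and not for common ones. The point is worth correcting before data are reviewed. It touches secondary aims only.

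**What to change.** **Side effects.** Reword (1)(b) as similar side effects, described by the between-arm difference with a 95% confidence interval: days for ileus duration, and a risk difference for rash, itching and nausea/vomiting. Avoid phrasing the aim as no difference detected, which is a result and not a hypothesis. State that no equivalence claim will be made unless a margin is written into the SAP before the first data review, which section 9 places at 20 subjects per arm.

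**Pain.** In section 7, replace or supplement the averages with the individual scores from the same electronic nursing record. Compute one proportion of scores up to 4 per patient over a pre-stated window, and summarise it in each arm. The documents give no window for pain scores; 48 hours, matching the primary outcome, is a suggestion. Make any between-arm comparison on the per-patient value, using the plan's own t-test/Mann-Whitney rule, so that repeated scores are not treated as independent.

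**Minor.** Add ileus duration, rash and itching to the same list, taken from the chart over the same period in both arms.

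**Cost.** SAP wording and a slightly longer abstraction from a record already in use. The side-effect conclusion becomes weaker than equivalent, and patients with few recorded scores will have imprecise proportions.

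### The secondary objective predicts lower medical utilization cost but measures only drug and supply acquisition cost, so it omits the staff time the plan gives as part of its rationale

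*Combined protocol and SAP*

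**What the plan says.** Section 2 (Objectives), secondary objective (2), sets two cost comparisons: "Compare the pharmacological costs and medical utilization costs of TAP block catheters versus single shot injection". Item (a) gives a direction for the second: "Anticipate lower medical utilization costs with single shot injection with liposomal bupivacaine TAP blocks". Item (b) gives the only measure: "Measured as acquisition cost of drugs and supplies".

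Section 3 (Background) explains why the catheter technique is demanding. The first items are equipment: "it is resource intensive requiring the use of two sterile peripheral nerve catheter kits, two CADD infusion pumps". Staff time follows. For nurses the item is "nursing time to replace the ropivacaine infusion cassette every 8-10 hours". The list then turns to physicians, for whom it names "30-40 minutes of physician time for block placement with additional physician time needed for ongoing catheter management". The same section compares drug prices per vial, "Although the expense of the Exparel is higher than a vial of ropivacaine", and then suggests that the costs and utilization tied to catheters may still exceed the price of one vial of Exparel.

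No other section widens the measure. Section 6 (Study Endpoints) lists PACU and hospital discharge times but attaches no cost to them. The data list in section 7 (Procedures Involved) includes PACU clearance time and length of stay, but no staff minutes, cassette counts or cost items. The statistical analysis plan, placed under section 8, contains no cost analysis, unit costs or costing perspective.

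**The concern.** Acquisition cost is a reasonable measure of the pharmacological half of the objective. It is only a partial measure of the utilization half, which carries the directional hypothesis. The plan's own account of catheter resource use includes nursing and physician time, and the measure gives that time no value.

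Followed as written, the trial would report an acquisition-cost result as a conclusion about utilization cost. The plan says Exparel is the dearer drug per vial, so the case for a lower total cost has to come from kits, pumps, cassettes and labour, and labour is left out. Because the data list has no item for staff time, it may also be hard to recover after the trial.

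**Working it through.** The plan states no cost figure, so there is nothing to reproduce. The check sets the rationale against the measure, works out when the omission matters, and then illustrates one omitted item.

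**Step 1: which rationale items the measure covers**

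| Item (section 3) | Covered by acquisition cost? |
|---|---|
| Two catheter kits | Yes, supplies |
| Ropivacaine cassettes and infused drug | Yes, drug and supplies |
| Two pumps | Possibly; the plan does not say whether pumps count as supplies |
| Nursing time for cassette changes | No |
| Physician time for placement, 30-40 minutes | No |
| Further physician time for catheter follow-up | No |

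**Step 2: when the omission changes the answer**

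Let A_C and A_E be the acquisition costs in the catheter and Exparel arms, and let L be the net labour cost, catheter minus Exparel.

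- Planned comparison: A_C − A_E.
- Comparison including labour: (A_C − A_E) + L.

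If L > 0:

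- If A_E < A_C, both comparisons favour Exparel, so the planned measure supports the hypothesis despite the omission.
- If 0 < A_E − A_C < L, the planned measure favours catheters while the fuller cost favours Exparel, so the sign is wrong.
- If A_E − A_C > L, both favour catheters.

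The last two cases cannot be told apart without L, so a higher Exparel acquisition cost is uninterpretable. The documents give none of A_C, A_E or L.

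L must be a net figure. Under section 7, single-shot patients also receive a bilateral block from the acute pain service and are seen for two days after surgery. The plan gives no placement time for the single-shot block, so the 30-40 minutes cannot be taken as the difference between arms.

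**Step 3: illustration for cassette changes**

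Inputs: one change every 8-10 hours and two pumps (section 3); 48 hours of infusion (assumed, from the two days that section 3 describes for many patients); 5-15 nurse minutes per change (assumed).

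Dividing 48 by 10 and by 8 gives 4.8 and 6 intervals. Replacements are fewer, because the first cassette is the starting one and none is needed at removal.

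- Every 10 h: changes at 10, 20, 30 and 40 h = 4.
- Every 8 h: changes at 8, 16, 24, 32 and 40 h = 5.

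The text does not say whether the interval covers both pumps or applies to each:

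| Reading | Replacements | Nurse time per patient |
|---|---|---|
| Interval covers both pumps | 4-5 | 4 × 5 = 20 min to 5 × 15 = 75 min (0.3-1.25 h) |
| Interval applies to each pump | 8-10 | 8 × 5 = 40 min to 10 × 15 = 150 min (0.7-2.5 h) |

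The overall range is about 0.3-2.5 nurse hours per catheter patient. Section 5 (Study Timelines) puts usual removal at postoperative day two or three, so some patients would need more.

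**The case against.** The strongest reply is that acquisition cost is a declared, narrow costing perspective on one secondary objective, and that it captures more than a first reading suggests. Kits, cassettes and infused drug are all counted, and pumps may be. Catheter duration varies between patients, so the measure is not simply a price list fixed by arm. PACU time and length of stay are recorded, so some utilization is observed. All of this stands, and it limits the point to the missing staff time.

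Three stronger readings are tempting, and the documents do not support them.

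- A reader might infer that the measure cannot test the hypothesis at all. If catheters need more net labour, the omission works against the hypothesis, so a lower Exparel acquisition cost would support it.
- A reader might infer that the result will come out reversed because Exparel costs more. The stated price comparison is with a single vial of ropivacaine, not with the catheter arm's bolus, repeated cassettes and two kits. Without prices, reversal is possible but not shown.
- A reader might treat all placement and follow-up time as extra catheter cost. Single-shot patients also have a block and two days of visits, so only the difference counts, and it is not given.

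The reply does not remove the mismatch. The objective and hypothesis are worded as medical utilization cost, and no part of the plan says the conclusion will be restricted to acquisition cost.

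**Conclusion.** The point holds as a mismatch between the hypothesis and its measure. The cost comparison can support a statement about drug and supply acquisition cost. It supports a statement about medical utilization cost only if Exparel's acquisition cost is lower and net labour is no lower with catheters. If Exparel's acquisition cost is higher, the result is uninterpretable for utilization and could have the wrong sign.

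The size of the distortion is unknown. The illustrative 0.3-2.5 nurse hours per catheter patient rests on assumed values for duration and minutes per change, spans both readings of the change interval, and covers cassette changes only. The point should be addressed before the cost comparison is reported. It concerns a secondary objective and leaves the primary outcome, its analysis and the sample size untouched.

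**What to change.** Choose one of two changes.

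(a) Limit the objective, the hypothesis and the eventual conclusion to drug and supply acquisition cost, and state whether pumps are included. This costs only a wording change.

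(b) Keep the utilization objective and widen the measure. In both arms, take from the EMR and pharmacy records the number of cassette replacements, block placement time, all acute pain service visits (including the two days of visits in the single-shot arm) and pump use. Multiply each count by stated minutes where needed and by a stated unit cost, and show a sensitivity range. Report acquisition cost as a separate line so that the two components remain visible.

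Option (b) costs some extra data extraction and a short table of unit costs. Its weakness is reliance on assumed minutes and wage rates, which is why the range should be reported with the result.
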